# 7.1.2 Secondary Analyses

Comparison of PLES versus PLES Waiting List: Appropriate statistical methods will be used to make within-person comparisons using the same measures as above.

Comparison of PPCP versus PLES at 32 weeks.

Outcomes after commencing each of the two interventions (16 weeks post randomisation for PPCP, and 32 weeks post-randomisation for PLES) will be compared using similar statistical methods as described in the updated primary analysis.

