#### 4.1 Statistical design

The study uses a waitlist design. Participants are randomised to two trial arms: (i) 16 weeks waitlist followed by 16 weeks PLES treatment or (ii) 16 weeks PPCP treatment. The 16-week comparison between the two trial arms will inform the primary efficacy objective (PPCP vs waitlist). The design includes PLES treatment after waitlist, to enable assessment of the secondary relative efficacy objectives (PPCP vs PLES; PLES vs waitlist). Outcome assessments take place before randomisation (baseline), after 16 weeks intervention in either trial arms, and at 32 weeks after PLES intervention in the waitlist/PLES arm. Note that the 16 week assessment in the waitlist arm measures the outcome after waitlist treatment as well as providing the starting value for the PLES outcome assessment at 32 weeks.

The design allows for longer-term follow-up of the active treatments (PPCP and PLES) at 32 weeks and 48 weeks respectively. However, these extra assessments are not for the purposes of the current

trial evaluation. They are described here, but are not included in the analysis plan and will not be reported in the main trial paper.

The health economic evaluation will be a within-trial cost-consequences analysis from a societal perspective of PPCP versus a waitlist control comparator. Secondary objectives: to undertake an assessment of the potential impact of PPCP on long-term costs to the public sector arising from conduct disorder in childhood and adolescence; to undertake a within-trial cost-utility analysis of PPCP versus waitlist control from an NHS/social care services perspective.

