# Measures Pack C: Follow Up 32 weeks after randomisation in PPCP arm, 48 weeks after randomisation in PLES arm (so for both, 16 weeks after treatment ends)

Adapted Affective Reactivity Index (ARI-P)
Child Quality of Life Assessment (CHU9D)
Child and Adolescent Service Use Schedule (CA-SUS)
Eyberg Child Behaviour Inventory (ECBI)
Generalised Anxiety Disorder Assessment (GAD-7)
Inventory of Callous-Unemotional traits (ICU)
Observation of Parent-Child Interaction (OBS)
Parent Account of Child Symptoms Conduct Problems (PACS CP)
Parent Account of Child Symptoms Oppositional Defiance Disorder
section (PACS ODD)
Parent Account of Child Symptoms ADHD (PACS ADHD)
Parent Account of Child Symptoms Expressed Emotion rating (EE)
Parent Quality of Life (EQ-5D-3L)
Patient Health Questionnaire (PHQ9)
Quality of Attachment Relationships (QUARQ)
Brief Self Efficacy Scale (BPSES)
Short Alabama Parenting Questionnaire (APQ)
Parent Strengths & Difficulties Questionnaire (SDQ)
Visual Analogue Scale (VAS)
York Assessment of Reading for Comprehension (YARC)
You and Your Partner (Moffitt) (YYP)

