#### TOTAL PARENT-CHILD INTERACTION TIME 25 minutes

#### 6. INTERVENTIONS

Participants will be randomly allocated to one of two groups:

Group 1: Waiting list followed by Parent-Led Education and support (PLES) designed to provide parents with support in parenting a child with persistent conduct problems. Research into parents' preferences for how to receive help indicate that many prefer self-administered formats (Metzler, Sanders et al., 2012). Following initial assessment, families randomised to this arm of the trial will wait 16 weeks and then be re-assessed before receiving the treatment. Inclusion of this waitlist period will enable the study to answer the question whether 1) the more intensive treatment is superior to no treatment (the primary aim of the trial) and also, as a secondary analysis, 2) whether the PLES intervention is superior to no treatment (waitlist). The study team will maintain close and frequent contact with the families while they are awaiting treatment and provide a contact number should they wish to speak to one of the researchers. NIHR and the programme steering committee have approved this change. Currently this population receive no treatment at all so it is felt that this is ethical. The PLES condition in this study will provide parents with a range of self-administered formats (see below) with additional advice being provided weekly by a CAMHS practitioner, in response to parents' own questions. Parents will have access to an online parenting programme which covers key aspects of parenting skills which have been shown to be effective in reducing child behaviour problems. The practitioner will be familiar with the online programme and will be available to talk over parents' questions about it. Parents will also be provided with other sources of information regarding children and their parents, such as books, and specifically prepared reading, which cover topics which are additional to the online programme and provide alternative approaches. These include reflecting on children's thoughts and feelings, and how parents decide when to listen, when to comfort, and when to ensure they behave as expected. The practitioner will be available to talk over all the written and online materials. It is also designed to be an informative and cheaper alternative to the intensive personalised programme, PPCP, so that a finding of no difference between the intervention arms will have service implications. A trained practitioner will be assigned to the parents over a 16 week period, so that they can meet, where possible online, every week.

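### The PPCP v PLES comparison sets blinded week-16 PPCP outcomes against unblinded week-32 PLES outcomes, so treatment cannot be separated from time, and a null result cannot carry the service implications Section 6 gives it

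*Protocol*

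**What the plan says.** All references are to the Protocol.

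- **Section 7.1.2** titles the comparison "Comparison of PPCP versus PLES at 32 weeks". Its text says: "Outcomes after commencing each of the two interventions (16 weeks post randomisation for PPCP, and 32 weeks post-randomisation for PLES) will be compared", and adds that this will be done "using similar statistical methods as described in the updated primary analysis". That analysis, in Section 7.1.1, is an ANCOVA with an arm indicator, sex, age and the randomisation stratifier.
- **Section 4.1** describes the waitlist arm's week-16 assessment as also "providing the starting value for the PLES outcome assessment at 32 weeks". It places the PPCP week-32 assessment outside the analysis plan.
- **Measures Packs B and C** both contain PACS. PLES families receive Pack B at week 32. Pack C is headed "Follow Up 32 weeks after randomisation in PPCP arm, 48 weeks after randomisation in PLES arm".
- **Section 9.2.2** says that, after the design change, only week-16 outcome collection and analysis can stay blind.
- **Section 6** presents PLES as a cheaper alternative, "so that a finding of no difference between the intervention arms will have service implications".
- **Section 9.2.1** sizes the trial for PPCP against waitlist at 16 weeks, with a target of 0.4 SD (0.16 PACS points) that it regards as clinically significant.
- **Section 4.2 (Revised Study Plan)** reports 40 participants per arm with 16-week outcomes. It says comparisons with PLES will not be blind and, depending on attrition, may be only descriptive.

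**The concern.** The title and the text of Section 7.1.2 describe different analyses. Both can be run, because PACS is scheduled at week 32 in both arms. The text's version matches the arms on time since starting treatment, but it gives up the common time since randomisation that protects a randomised comparison. At assessment, PLES families are 16 weeks further on, have had one more assessment and have had longer to drop out. They are also assessed unblinded, whereas the PPCP outcomes are blinded.

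Any spontaneous improvement over weeks 16 to 32 would be credited to PLES. Any spontaneous worsening would count against it. The protocol does not mention this.

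The second problem is what the result is to be used for. If no difference is taken to have implications for services, a small, non-concurrent comparison with no margin could be read as showing that the cheaper programme does as well.

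**Working it through.** **1. The protocol's own figure.** Inputs from Section 9.2.1: 0.4 SD, 80% power, alpha 0.05 (two-sided reproduces it), t-test, 20% attrition. The normal-approximation formula gives n per arm = 2(1.96 + 0.842)²/0.4² = 98.1, rounded up to 99, so 198 in total. Inflated, 198/0.8 = 247.5, or 248. Both figures reproduce. They concern PPCP v waitlist, and no calculation is given for PPCP v PLES.

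**2. What the contrast estimates.** Let t16 and t32 be the change from baseline expected without treatment, and P and L the effects of PPCP and PLES 16 weeks after starting.

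- PPCP at week 16: baseline + t16 + P
- PLES at week 32: baseline + t32 + L
- Difference: (P − L) + (t16 − t32)

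The difference equals P − L only if t16 = t32.

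**3. Can the planned model separate them?** The original mixed model in Section 7.1.1 uses five arm-by-time cells: waitlist at 0 and 16, PLES at 32, PPCP at 0 and 16. Separating time at week 32 from the PLES effect takes six parameters (intercept, arm, t16, t32, P, L), but the design matrix has rank 5. Checking each contrast:

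| Contrast | Estimable? |
|---|---|
| P (PPCP v waitlist at week 16) | yes |
| L | no |
| P − L | no |
| (P − L) + (t16 − t32) | yes |

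The ANCOVA named in Section 7.1.2 does no better: with one outcome per family, arm and assessment week coincide exactly. This result needs no assumed size of drift.

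**4. Size of the bias.** It is t16 − t32, carried one for one into the estimate. The protocol gives no figure for untreated change over weeks 16 to 32. Purely as an illustration, a drift of 0.1 to 0.3 SD would shift the estimate by 0.04 to 0.12 PACS points, using the implied SD of 0.16/0.4 = 0.40. The sign is also unknown.

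**5. What a zero estimate could exclude.** The unadjusted 95% CI half-width in SD units is t(0.975, 2n − 2) × √(2/n).

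| Per arm | Half-width, SD | PACS points |
|---|---|---|
| 99 (planned completers) | 0.28 | 0.112 |
| 40 (Section 4.2) | 1.99 × 0.2236 = 0.445 | 0.178 |
| 32 (assumed further 20% loss) | 0.50 | 0.20 |

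Baseline adjustment multiplies the half-width by about √(1 − r²). At an assumed r = 0.5 and 40 per arm, this is 0.445 × 0.866 = 0.385 SD (0.154 points). The half-width falls below 0.4 SD only when r exceeds √(1 − (0.4/0.445)²), about 0.44. Unadjusted power to detect 0.4 SD at 40 per arm is 42%.

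**The case against.** The best defence is that the unequal weeks are deliberate. Sections 4.1 and 7.1.2 and the measures packs all aim at the outcome 16 weeks after starting each treatment, which is a sensible question. The title can be read as PPCP against PLES-at-32-weeks, and the next sentence gives both time points. This stands: the choice is not a slip. But it is valid only if nothing apart from treatment changes between weeks 16 and 32, and the protocol neither states nor can test that.

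The protocol has also demoted the comparison. Formal reporting is limited to PPCP v waitlist at 16 weeks, and PLES analyses may be descriptive. This lowers the severity. However, the stated reasons for caution are attrition and loss of blinding, not time. Section 7.1.2 still plans the comparison and the Section 6 sentence remains.

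The same-week comparison has its own weakness. At week 32 PPCP is 16 weeks past its primary endpoint while PLES has just ended. Section 2 reports that 35% of cases who had done well in the earlier study later declined, and it describes PPCP booster work over a further 3 months. The week-32 contrast therefore answers a different question and does not identify P − L either. For that reason it belongs beside the planned contrast, not in place of it.

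Finally, the Section 6 sentence is background rationale, not a decision rule, and the objective in Section 3.1 is superiority. No equivalence margin is therefore required; what is unsupported is the inference from a null result.

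**Conclusion.** The point holds as a modest one. The comparison described in Section 7.1.2 estimates the treatment difference plus any change over weeks 16 to 32 that would have occurred anyway. It also mixes blinded with unblinded outcomes, and its title does not match its text. The non-estimability follows from the design alone. At 40 per arm a zero estimate has an unadjusted half-width of 0.445 SD, or 0.385 SD if r = 0.5 is assumed. It would thus exclude 0.4 SD narrowly or not at all, and further attrition would make this worse.

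Three stronger readings are tempting, and the documents do not support them:

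- **That the bias is a known, large share of the 0.4 SD target.** Any such percentage rests on an assumed drift; the protocol supplies none.
- **That early regression to the mean is credited only to PPCP.** Entry does require a high PACS score. But Section 7.1.2 does not say that week 16 is the PLES baseline for this comparison, and the wording in Section 4.1 fits the within-person PLES v waitlist analysis. With a pre-randomisation baseline, both arms carry the selection effect.
- **That 0.4 SD should serve as a margin between PPCP and PLES.** It was set for PPCP against no treatment. As a margin it could let PLES pass after losing nearly all of PPCP's targeted benefit.

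**What to change.** 1. **Section 7.1.2.** Correct the title. State that the week-16 v week-32 contrast is non-concurrent, assumes no change over weeks 16 to 32 apart from treatment, sets blinded against unblinded outcomes, and is exploratory.
2. **Sections 7.1.2 and 4.1.** Report alongside it the randomised comparison at week 32 in both arms, using PACS from Pack C for PPCP and Pack B for PLES. Adjust both arms for pre-randomisation PACS and label it 'immediate PPCP' v 'wait then PLES'. Amend Section 4.1, which leaves the PPCP week-32 data out of the analysis plan.
3. **Section 6.** Delete the sentence on no difference. Alternatively, say that estimates and 95% CIs will be reported and that a non-significant result will not be read as equivalence. Do not use 0.4 SD as a margin.

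**Cost.** No new data collection: the changes are to wording, plus one added analysis and a small widening of the analysis plan's scope. The week-32 contrast compares strategies (PPCP 16 weeks past its primary endpoint, possibly with booster sessions, against PLES just ended), and all week-32 data are unblinded. Both limits should be stated with the result.

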## 4.2 Revised Study Plan

In discussion with the funder it was decided to stop recruitment on 31st August 2024 despite not reaching the intended sample size. It was agreed to follow up participants to 16 weeks and then lock these data and analyse only the 16 week outcomes as part of the NIHR funder report. We will formally report on outcome differences between PPCP and waitlist arms at 16 weeks. 32 week outcomes will be collected beyond the end of the original funding period which was 31st April 2025; data will now be collected until 31st August 2025. By necessity future analyses of differences with PLES will not be blind. Depending on attrition rates it might also be only possible to provide descriptive analyses involving the PLES arm. However, the team is committed to ultimately publishing all outcome data collected as part of this study.

By the end of December 2024, we had recorded the outcomes of 80 trial participants at the 16-week-from-randomisation stage. This means that comparisons will be made between 40 participants who have completed the PPCP intervention and 40 participants who have been on the waiting list, which is the primary outcome objective.

[figure not shown]
However, in view of the revised sample size (numbers of participants being around 30-40% of those predicted) the study may be better described as a Pilot and Feasibility Study, rather than a full RCT.

NIHR has agreed a proposal to conduct two additional qualitative interviews exploring the experience of study participants and that of the practitioners in order to optimise learning for the NHS. These will be conducted and analysed as described in Section 7.3 Process Evaluation.

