### 7. METHODS of DATA ANALYSIS

#### 7.1 Quantitative Analysis

# 7.1.1 Primary Analysis

The original plan based on meeting the recruitment target and having access to a locked database containing relevant baseline, 16 week and 32 week variables was as follows:

All analysis will be according to the intention-to-treat principle. Characteristics of the treatment groups will be described at baseline. Preliminary analysis will investigate the pattern of missing outcome data. The statistical analyses of the primary outcome measure (PACS) and the secondary measures will estimate three treatment effects to address the primary and secondary objectives of this study. Briefly, we use linear mixed models to estimate relevant contrasts. Continuous outcome variables such as PACS will be analysed in long format, for example the PACS variable will consist of stacked measures of (i) PACS recorded at baseline in either arm, (ii) PACS recorded at 16 weeks in either arm, and (iii) PACS recorded at 32 weeks in the waitlist/PLES arm only. The models will contain a dummy variable for PPCP trial arm (PPCP), a dummy variable for the 16 week assessment time point (W16), the product of these two dummy variables (PPCP x W16), and a dummy variable indicating the 32 week assessment time point in the waitlist/PLES arm (W32), binary participant sex and continuous age as known predictors of outcomes, dummy variables for delivering PLES or PPCP interventions and randomisation stratifiers. With this parameterisation the regression coefficient of PPCP x W16 represents the treatment effect of PPCP vs waitlist at 16 weeks; and the other treatment effects can be estimated by estimating relevant contrasts of the regression coefficients. To account for the correlation between the two or three repeated measures on the same participant (and to acknowledge that the contrast between waitlist and PLES is a within-trial arm comparison) a subjectvarying random intercept will be included.

The analyses will remain valid in the presence of missing values in the outcome variables, provided the variables that predict missingness are included in the respective linear mixed model (missing at random, MAR, assumption).

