After it was agreed with the funder to stop recruitment and only formally report on the PPCP vs waitlist comparisons at 16 weeks as part of this study, the SAP had to be amended. Specifically, the proposed analyses were simplified so that they could be carried out after the 16 week data was locked (i.e. not requiring access to any 32 week data:

All analysis will be according to the intention-to-treat principle. Characteristics of the treatment groups will be described at baseline. Preliminary analysis will investigate the pattern of missing outcome

data. The statistical analysis of the primary outcome measure (PACS) and the secondary measures (ECBI etc) will estimate the effect of PPCP relative to waitlist at 16 weeks post randomisation. Briefly, we will use an ANCOVA approach to estimate relevant trial arm differences. The models will contain a dummy variable for the PPCP trial arm and include covariates for binary participant sex and continuous age as known predictors of outcomes and for the randomisation stratifier.

These simplified analyses will remain valid in the presence of missing values in the outcome variables, provided the variables that predict missingness are included in the respective linear mixed model (missing at random, MAR, assumption).

A full statistical analysis plan (SAP) will be developed by the trial statisticians and agreed with the principal investigators and TSC before any post randomisation data is seen by either party.

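### PPCP v PLES is sent to the 16-week ANCOVA, which has no place for the PLES arm's week-16 PACS; if week-32 loss depends on that score, the contrast is biased

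*Protocol*

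**What the plan says.** Protocol 7.1.1 sets out two plans.

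- **Original plan.** One linear mixed model stacks PACS at baseline, week 16 and (waitlist/PLES arm only) week 32. All three treatment contrasts come from that model, and "a subjectvarying random intercept will be included".
- **Amended plan.** After recruitment stopped, "the proposed analyses were simplified so that they could be carried out after the 16 week data was locked". For PPCP v waitlist at week 16, "we will use an ANCOVA approach to estimate relevant trial arm differences". The terms are listed: "The models will contain a dummy variable for the PPCP trial arm and include covariates for binary participant sex and continuous age", plus the randomisation stratifier. No earlier PACS score is named. The paragraph on missing data still makes validity under missing at random depend on a linear mixed model.

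Section 7.1.2 then says that the outcomes of the two interventions "will be compared using similar statistical methods as described in the updated primary analysis". The time points it gives for this comparison are "16 weeks post randomisation for PPCP, and 32 weeks post-randomisation for PLES". For PLES v waiting list it asks only for appropriate within-person methods.

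Section 4.1 notes that the week-16 assessment in the waitlist arm also supplies the starting value for the PLES outcome. Section 4.2 warns: "Depending on attrition rates it might also be only possible to provide descriptive analyses involving the PLES arm".

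**The concern.** The amended 16-week analysis had to run at a data lock that excluded week 32. An analysis of PPCP v PLES cannot run until week-32 data exist, so the stated reason for the simpler method has gone by then. Section 7.1.2 carries the simpler method over all the same.

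This matters for missing data. An ANCOVA with one outcome per family uses only the PLES-arm families who are seen at week 32. Their week-16 PACS, recorded just before PLES starts, is likely to predict both the week-32 score and who is lost. It cannot simply be added as a covariate, because in the PPCP arm the week-16 score is the outcome. A repeated-measures model is the natural way to use it.

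If families who do badly on the waiting list are lost before week 32, those who remain make PLES look better than it is. Section 6 presents PLES as the cheaper option and says that finding no difference would have consequences for services. Where PPCP is truly better, a bias of this kind pushes towards that finding.

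**Working it through.** **Scale.** Section 9.2.1 uses 0.4 SD, 80% power and alpha 0.05 (two-sided assumed). Per arm, n = 2 × (1.960 + 0.842)² / 0.4² = 98.1, rounded up to 99, so 198 in total. With 20% attrition, 198 / 0.8 = 247.5, so 248. Both stated figures reproduce; the sample size is not in dispute. The same section equates 0.4 SD with 0.16 PACS points, so 1 SD = 0.16 / 0.4 = 0.40 points.

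**Assumptions that are not in the protocol.** Week-32 loss in the PLES arm is 20% or 40%. The log-odds of loss rise by 0.5 or 1.0 per SD of week-16 PACS. Correlations between visits are 0.5 or 0.7 throughout, or unequal: 0.5–0.6 (weeks 0–16), 0.6–0.7 (weeks 16–32) and 0.45–0.55 (weeks 0–32). There are 40 families per arm (section 4.2). Sex, age and stratifier are left out because they are common to all methods.

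**Step 1: how far the retained families differ.** Let m be the amount by which the mean week-16 PACS of families still seen at week 32 lies below the mean of the whole arm, in SD. Integrating the logistic loss model over a standard normal week-16 score gives:

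| Loss | Log-odds 0.5 | Log-odds 1.0 |
|---|---|---|
| 20% | 0.096 | 0.173 |
| 40% | 0.189 | 0.332 |

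**Step 2: ANCOVA as listed.** Bias = r(16,32) × m.

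- Smallest: 0.5 × 0.096 = 0.05 SD, or 0.02 PACS points.
- Largest: 0.7 × 0.332 = 0.23 SD, or 0.09 points, over half of the 0.16-point target.

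**Step 3: ANCOVA with baseline PACS added.** Bias ≈ [r(16,32) − b × r(0,16)] × m, where b is the pooled slope on baseline, about the mean of r(0,16) and r(0,32).

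- Smallest (all correlations 0.7): (0.7 − 0.7 × 0.7) × 0.096 = 0.02 SD.
- Largest (0.5, 0.6 and 0.45, so b = 0.475): (0.6 − 0.475 × 0.5) × 0.332 = 0.12 SD, or 0.05 points.

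**Step 4: simulation.** With equal correlations and 20,000 trials per scenario, bias was 0.049 to 0.233 SD as listed, 0.021 to 0.082 SD with baseline added, and within 0.002 SD of zero for a likelihood-based repeated-measures model. With the unequal correlations and 6,000 trials per scenario, the baseline-adjusted ANCOVA gave 0.03 to 0.12 SD and the repeated-measures model stayed within 0.003 SD of zero. With loss unrelated to week-16 PACS, every method was unbiased to within 0.002 SD.

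**Step 5: precision.** Empirical SE in SD units at 20% loss:

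| Method | Correlation 0.5 | Correlation 0.7 |
|---|---|---|
| ANCOVA as listed | 0.24 | 0.23–0.24 |
| ANCOVA plus baseline | 0.21 | 0.17 |
| Repeated measures, common baseline mean | 0.21 | 0.17 |
| Repeated measures, separate baselines | 0.23–0.24 | 0.18 |

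The gain in precision comes from adjusting for baseline. The repeated-measures model adds almost nothing to that.

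**The case against.** **The wording is loose, and a SAP may settle it.** Section 7.1.2 asks only for similar methods, and 7.1.1 describes its model briefly and promises a full SAP. This stands as a limit: the protocol does not forbid a repeated-measures model. It does point to a specific method, though, and the terms listed for that method leave no place for the week-16 score.

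**The original plan also assumed that the recruitment target would be met.** That is so, and the shortfall remains at week 32. It is a reason to keep the covariance model modest. It is not the reason 7.1.1 gives for simplifying.

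**The size depends on undocumented assumptions.** This stands. The only attrition figure in section 9.2.1 is 20%, planned for the 16-week comparison. At that rate, with baseline PACS added, the bias is about 0.02–0.06 SD against an SE near 0.2. If families doing well are the ones lost, the sign reverses.

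**Stronger readings that a reader might infer.**

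- *That the contrast is biased outright.* The documents say nothing about who is lost, so the bias is conditional.
- *That all PLES contrasts ignore week 16.* Section 7.1.2 asks for within-person comparisons for PLES v waiting list.
- *That both arms depend on attendance at week 32.* Only the PLES arm does; PPCP is assessed at week 16.
- *That the original model also needs its "dummy variables for delivering PLES or PPCP interventions and randomisation stratifiers" removed.* The phrase is ambiguous. It may mean practitioners, since 7.3 counts three PPCP and two PLES clinicians, and it stands in superseded text.

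**Conclusion.** The point holds in a conditional form. Section 7.1.2 gives PPCP v PLES a method adopted for a reason that does not apply to it, and that method leaves out the PLES arm's week-16 PACS. The missing-at-random statement in 7.1.1 also refers to a mixed model that the amended analysis no longer uses.

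If week-32 loss in the PLES arm depends on week-16 PACS, the contrast is biased by about 0.05–0.23 SD as listed, or about 0.02–0.12 SD with baseline PACS added. The bias favours PLES if families doing badly are lost. These figures rest on the assumed loss, log-odds and correlations. A repeated-measures model is about unbiased under the same assumptions. The case rests on missing data, not on precision.

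The priority is modest. The comparison is secondary, will be unblinded (sections 4.2 and 9.2.2) and may end up descriptive. Because the 16-week results will be known by then, it is better to fix the model now. The change does not alter the fact that the two arms are assessed 16 weeks apart.

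**What to change.** In 7.1.2, state that once 32-week data are locked, PPCP v PLES and PLES v waitlist are estimated as contrasts from a likelihood-based repeated-measures model of baseline, week-16 and (waitlist/PLES arm) week-32 PACS in all randomised families. This restores the approach of the original plan. A common baseline mean and an unstructured covariance are preferable. They differ from the original specification, which has a random intercept and a PPCP main effect, and so separate baselines. Align the missing-at-random sentence in 7.1.1 with the model actually used.

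The cost is a paragraph of wording and slightly more analysis work; no new data are needed. An unstructured covariance for three visits has 6 parameters against 2 for a random intercept, so 4 more to estimate at about 40 families per arm.
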